8.2 Describe the procedures for compensating research-related injuries

Study-related injuries are not expected. However, for the minimal risks of a slight nasal bleeding originating after sampling for RT-qPCR or some complication in the placement of a nasogastric tube in intubated patients, immediate management of the lesion will be performed, and all expenses related to this will be covered by the State of Honduras. In the event of a hypersensitivity reaction to thymic peptides (Unicahsina), timely management will be given and the necessary medication expenses for the specific event will be covered by the State of Honduras.

SECTION 9 - INFORMED CONSENT

The informed consent process will start from the recruitment of the participants. Once the potential study participants have been identified, we will proceed to report on the objective and the methodology that will be used to answer the research questions. During the discussion of the consent form, it will be ensured that the participant has the necessary time to fully understand all the interventions to which he/she will be exposed. The participants will be allowed to ask the questions that are necessary to clear any doubts. It will be emphasized that the decision to be part of the study is absolutely voluntary, in addition to the fact that participant can withdraw at any time without incurring in any penalty. If the participant agrees, he/she will be asked for a signature or fingerprint. The participant will receive a copy of the form.

During the duration of the research, the participant will continue to be informed about their clinical evolution, new risks, changes in procedures, dose modification, extension, or completion of the study (prior authorization by the Ethics Committee). In addition, the ability of the patient to consent and reaffirm their willingness to remain in the study will be continuously evaluated.

REFERENCES:

- 1. McIntosh K. Coronavirus disease 2019 (COVID-19). Hirsch M. 26 Mar 2020,https://www.uptodate.com/contents/coronavirus-disease-2019-COVID-19


PROTOCOL

VERSION B

SECTION 1 – TITLE, PURPOSE AND JUSTIFICATION

- **1.1 Title.** Safety and Efficacy of Thymic Peptides in the Treatment of Hospitalized COVID-19 Patients in Honduras.
- **1.2 Study Purpose.** To determine if thymic peptides (Unicahsina) are a new therapeutic option for the treatment of patients infected by COVID-19 in order to improve their clinical prognosis.
- **1.3 Justification**. Coronaviruses are important pathogens in humans and animals, causing respiratory tract and lung parenchymal infections. In late 2019, a novel coronavirus was identified as the cause of a series of pneumonia cases in Wuhan, a city in Hubei province in China (1). The infection spread rapidly, leading to an epidemic throughout China, followed by an increasing number of cases in other countries, affecting all continents except Antarctica (1). WHO declared COVID-19 a pandemic on March 11, 2020 (2). The virus is currently referred to as Severe Acute Respiratory Syndrome Coronavirus 2 (SARS-CoV-2) and the disease caused by the virus is known as COVID-19.

At the time of writing this protocol, more than 5,584,091 cases of COVID-19 have been reported worldwide (3). This is largely due to the ease with which this virus is transmitted. The primary mechanism of spread is person-to-person transmission, which occurs primarily by respiratory droplets (1). Transmission of SARS-CoV-2 via fomites is plausible as it has been shown to remain viable on surfaces for hours and even several days (4).

The coronavirus that causes COVID-19 is a betacoronavirus of the same subgenus as SARS-CoV (5). The incubation period is estimated to be 14 days after exposure, with most cases occurring between 4 and 5 days (6-8). The disease is mild in 81% of cases, severe in 14% and critical in 5% (9). The overall mortality rate is 2.3% (9). The clinical course is characterized by fever (99%), fatigue (70%), dry cough (59%), anorexia (40%), myalgia (35%), dyspnea (31%) and sputum (27%) (10). Pneumonia appears to be the most serious manifestation of infection, characterized mainly by fever, cough, dyspnea and a bilateral pulmonary infiltrate (visible on imaging) (7, 10-12).

Global statistics show that mortality due to COVID-19 increases significantly with age. Pediatric patients under 9 years of age present mild cases with practically zero mortality (13). Between 9 and 39 years of age, statistics indicate a mortality of approximately 0.2% (13). In the age range between 40 and 69 years, the rate oscillates between 1.3 and 3.6% (13). Above 70 years of age, deaths due to COVID-19 increase exponentially, reaching 8% of cases (13). Patients over 80 years of age are the highest risk group with a mortality rate of 14.8% (13).

This remarkable statistical difference in morbidity and mortality is consistent with a biological process that has so far been scarcely addressed: involution of the thymus. This retrosternal gland is part of the primary lymphoid organs, playing an important role in the maturation and differentiation of T cells to CD4+ and CD8+ subtypes, in addition to secretion of cytokines that mediate the immune response (14). Involution follows a characteristic pattern in which there is a progressive loss of function from the first year of life (15). Between 35 and 45 years of age this process accelerates, losing up to 30% of its function in a decade (15). Finally, after the age of 65 it regresses and is replaced in its totality by adipose tissue (15).

Ferman-Cano et al. suggest that the relative protection observed in the infant population with COVID-19 could be explained by the influence of the thymus. Based on this background and the evident relationship between the age ranges in which thymus involution occurs and the exponential increase in mortality, we propose that at older ages there is a greater deficiency of thymic factors, whose replacement represents a therapeutic mechanism to be explored. In this context, thymic peptides stand out as potent candidates given their immunogenic properties and proven safety.

Thymomodulin is a set of low molecular weight peptides of less than 10,000 Daltons, derived from the acid lysis of calf thymus (16). It has been shown that modulates the maturation and function of T lymphocytes and favors the expression of B cell surface markers (16,17). In vitro, thymomodulin has been shown to possess a myelopoiesis-inducing effect in the bone marrow, stimulating granulocyte and macrophage colonies (18). In addition, in murine studies it has been shown to produce an increase in serum thymic hormone (19).

In clinical studies, thymomodulin has proved to reduce the number of recurrent respiratory infections in children (20). This improvement is associated with a higher CD3 + and CD4 + cell count, increased neutrophilic function and salivary IgA levels (21, 22). It also has multiple reports on its safety and efficacy in patients with immune imbalance, in pathologies such as chronic bronchitis (23-25), bronchial hyperresponsiveness (26), asthma (27-29), food allergy (30, 31), atopic dermatitis, immunosuppression by chemo or radiotherapy for neoplasms (32, 33), initial phases of AIDS (34-36) and senectitude thymic involution (19,37,38).

In geriatric patients, studies prove safety at high doses (19), an increase in the number of lymphocytes, monocytes, IgA, IgG and IgM levels (37-40). Likewise, thymomodulin increases the production of free radicals due to alveolar macrophages (23). It is noteworthy to mention that it can even prevent and emend leukopenia in patients undergoing chemotherapy and radiotherapy (41), which has been proven in patients with breast and genitourinary tract cancer (42).

In studies of acute and chronic toxicity, it has been shown that thymomodulin does not possess teratogenic or embryotoxic effects (43). For this reason, it has a high potential for use during pregnancy.

Given the fact that the population most at risk of presenting severe disease and a higher mortality rate due to COVID-19 are immunosuppressed patients, older adults and/or those with comorbidities, effective therapeutic options with high safety profiles are needed. Currently there are no treatments available that meet these

requirements for disease management. Treatment options include protocols using chloroquine or hydroxychloroquine. The evidence in favor of its use remains controversial, since a number of adverse effects have been documented that could affect the most vulnerable population. They are contraindicated in patients with retinopathy (44), neuromyopathy and heart disease due to the possible increase in the QT interval (45).

Scientific evidence proves the absence of short or long-term adverse effects of thymomodulin, obtaining significant results in the treatment of patients with immunological vulnerability in various respiratory pathologies (23). Taking this into account, it can be considered a promising alternative to combat the COVID-19 pandemic. The following sections will discuss the methodology of the clinical trial that will be used to evaluate its efficacy as a therapeutic option.

Hypothesis

Oral administration of thymic peptides (Unicahsina) is a safe and effective therapy for the management of patients with COVID-19 respiratory onsets.

General Objective

To demonstrate the therapeutic efficacy and safety of thymic peptides (Unicahsina) in patients with COVID-19 respiratory disease.

Specific objectives

- 1. To evaluate the safety of thymic peptides (Unicahsina) by monitoring adverse events using the Common Terminology Criteria for Adverse Events Version 5.0 (CTCAE v5.0) and side effects using the General Assessment of Side Effects (GASE).
- 2. Determine the time to participant recovery, according to a clinical ordinal progression scale.
- 3. To perform survival analysis in patients diagnosed with COVID-19 and treated with thymic peptides (Unicahsina).

SECTION 2 - DESCRIPTION OF THE POPULATION

2.1 Number of participants: 20 participants.

2.2 Describe the population:

Patients with diagnosis of COVID-19 confirmed by RT-qPCR testing, viral antigen detection or antibody detection plus associated symptomatology. The study will be performed in patients over 20 years of age without distinction of sex, race, religion, or socioeconomic status. Since the population under 20 years of age presents mostly mild or asymptomatic symptoms, with a mortality rate between 0% and 0.2%, it was decided to exclude this age range.

This research will involve elderly patients and those with comorbidities. The current COVID-19 pandemic has shown that this group of patients has the highest mortality rate, exposing the need to discover safe and effective therapies. Therefore, and given the innocuous profile that thymic peptides possess, we consider their use in this population.

Should any of the participants decide to withdraw from the study voluntarily or request self-discharge, another patient will be added to the study until 20 patients have reached conclusion either by medical discharge or death within a 20-day hospitalization follow-up. Patient data will be used up to the date of voluntary withdrawal or self-discharge.

2.3 Criteria

Inclusion Criteria:

- 1. Confirmed case of COVID-19 by viral nucleic acid (RNA) detection, viral antigen detection, or detection of antibodies to the virus.
- 2. Participants that require hospitalization under Honduran Ministry of Health Guidelines for Clinical Management of COVID-19 Adult Patients: Stage IIb, defined as a patient with or without risk factors that presents with warning signs (shortness of breath, tachypnea), and altered inflammatory parameters.
- 3. Participants that present with at least one of the following: oxygen saturation level below 94 percent; complete blood count showing lymphopenia, neutrophilia, or both; positive C-reactive protein; chest radiography or CT scan with ground-glass opacities.
- 4. Male or female at least 21 years old.

Exclusion criteria

- 1. COVID-19 patients that do not require hospitalization under Honduran Ministry of Health Guidelines for Clinical Management of COVID-19 Adult Patients: phase IA (asymptomatic), phase IB (mild symptoms without risk factors), or phase IC (mild symptoms with risk factors).
- 2. Participants currently in other clinical trials evaluating experimental drugs.
- 3. Known history of allergic reactions to thymic peptides or calf thymus acid lysate derivatives.
- 4. Organ transplant recipients.
- 5. Women who are pregnant or breast feeding.

SECTION 3. PARTICIPANT RECRUITMENT

Patients who meet the inclusion criteria and are hospitalized in Honduran facilities designated for the care of patients with COVID-19, will be recruited. Patients over 20 years of age capable of giving their consent will be included. In case that the patient is unable to authorize participation, authorization will be requested from his legal representative.

Prior to their incorporation into the study, patients will be approached by the specialist or health personnel present on behalf of the Medical Research Group of the Catholic University of Honduras. In addition, there will be auxiliary methods with electronic devices that will allow telemedicine to be carried out between the principal investigators of the study and the potential participants. This last procedure will be carried out with encrypted methods that guarantee the confidentiality and anonymity of the patients. The purpose and procedures of the investigation will be explained, as well as clarifying any doubts that may arise. Once consent has been obtained, the clinical data registration will begin, and the application of the protocol will be coordinated with the treating physicians.

SECTION 4 - METHODOLOGY AND PROCEDURES

4.1 Study design

This is a single-arm, open-label, phase II clinical trial to evaluate the safety and efficacy of thymic peptides in the treatment of hospitalized COVID-19 patients in Honduras, at the Hospital de Santa Bárbara Integrado. A participant-level comparison will be made based on registry data of the Hospital de Santa Bárbara Integrado, after propensity score matching.

In total, 20 patients will be recruited from the designated hospital for COVID-19 patient care, including those who have signed informed consent and who meet the inclusion criteria. For the generation of the comparison group through data from clinical records, it will be carried out by authorization from the Hospital de Santa Bárbara Integrado, given its retrospective nature, without experimental intervention.

Clinical characterization

Once the protocol is started, the information corresponding to the general data, signs, symptoms, physical examination and laboratory values of each patient will be recorded daily in the data collection instrument. The record will be made on paper, which will be digitized and sent under encryption to the principal investigators every day.

As a quantitative method, the following laboratory findings will be considered to evaluate clinical progress, according to the requirement and availability of the hospital:

- Complete blood count
- C-reactive protein
- D-dimer
- Ferritin
- Procalcitonin
- Lactate
- AST

- ALT
- BUN
- Creatinine

Administration of thymic peptides (Unicahsina)

Thymic peptides (Unicahsina) will be administered in an oral dose of 250 mg per day. In the intubated patient, the administration will be done through a nasogastric tube. The presentation of thymic peptides (Unicahsina) will be in lyophilized form, which will be diluted in 50 ml of drinking water prior to administration. It should be administered on an empty stomach one hour before or two hours after a meal. If the patient is discharged, or if they need to be referred to an ICU, all the information will be gathered up to that moment and the administration of Unicahsina will be stopped.

Primary outcome measures

1) Time to participant recovery [Time Frame: During hospitalization for up to 20 days.]

Measured in days to clinical recovery that will be defined as the first day, during the 20 days after enrollment, on which a patient met the criteria for category 1, 2, or 3 on the eight-category ordinal scale. The categories are as follows: 1, not hospitalized and no limitations of activities; 2, not hospitalized, with limitation of activities, home oxygen requirement, or both; 3, hospitalized, not requiring supplemental oxygen and no longer requiring ongoing medical care; 4, hospitalized, not requiring supplemental oxygen but requiring ongoing medical care (related to Covid-19 or to other medical conditions); 5, hospitalized, requiring any supplemental oxygen; 6, hospitalized, requiring noninvasive ventilation or use of high-flow oxygen devices; 7, hospitalized, receiving invasive mechanical ventilation or extracorporeal membrane oxygenation (ECMO); and 8, death.

2) Number of participants with treatment related adverse events as assessed by the Common Terminology Criteria for Adverse Events Version 5.0 (CTCAE v5.0) [Time Frame: Up to 20 days]

Number of participants who experience adverse events \geq Grade 3, as defined by the CTCAE v5.0.

3) Number of participants with treatment related side effects as assessed by the General Assessment of Side Effects (GASE) [Time Frame: Up to 20 days]

Number of participants who experience severe side effects as defined by the GASE.

Secondary Outcomes measures

1) Overall survival defined as the time from the start of treatment until death due to any reason [Time Frame: Up to 20 days]

Time for overall survival will be measured in days.

Other complementary analyzes

Computerized axial tomography and chest radiography

A Computerized tomography without contrast will be performed, with the patient in the supine position and the image acquisition will be carried out at the end of inspiration. The following parameters will be requested to obtain axial images: 1.25 mm thick, 1.25 mm interval, 120 kVp. If it is possible, chest radiographs will be requested in posteroanterior projection. However, in patients whose clinical condition warrants it, anteroposterior radiography will be considered. The images will be obtained at the moment of maximum inspiration, either with instruction to the patient or by controlling the ventilator console in the case of intubated patients.

The tomographic or radiographic findings will be interpreted using the scoring system previously described by Cai et al (46). After the analysis by the assigned radiologist of the hospital center, the data generated by CT or X-ray will be submitted to two independent radiologist physicians, both blinded to the corresponding group of participants and the corresponding clinic. These specialists will assign a Pulmonary Score 1 (SP1) according to the findings they observe, based on three categories:

- 1 = Normal attenuation
- 2 = Ground-glass opacity
- 3 = Consolidation

Each lung will be divided into 3 zones with limits defined as follows:

Upper zone: area above the level of the carina.

Middle zone: area between the level of the carina and the inferior pulmonary vein.

Inferior zone: area below the level of the inferior pulmonary vein.

In this way, a total of 6 pulmonary areas will be delimited, each of which will receive a score according to the following scale of distribution of compromised lung parenchyma or Pulmonary Score 2 (SP2):

- 0 = Normal
- 1 = 1% to 25% involvement
- 2 = 25% to 50% involvement
- 3 = 50% to 75% involvement
- 4 = More than 75% involvement

The scores of each lung area will be summed to obtain the Total Affectation (AT) grade. Finally, AT will be multiplied by SP1 to obtain the Total Cumulative Scale (ETA), which comprises a range from 0 to 72. A change of "Improvement" on CT or chest X-ray will be defined as an ETA lower than the previous value obtained at the start of treatment or from the previous imaging studies. A "worsening" change will be defined as an ETA greater than the previous value obtained at the start of treatment or previous imaging studies. The stability of the picture will be defined as "Constant" when the ETA is equal to the previous value obtained at the beginning of treatment or from previous imaging studies.

Statistical Analysis Plan

All quantitative data will be described using parameters such as the mean \pm standard deviation, or as the median (minimum and maximum). Qualitative data will be described by the number of cases (proportion%). Patient characteristics will be compared using the chi-square test or Fisher's exact test for categorical data. For continuous variable data, the Wilcoxon test or Student's t test will be employed. The analysis of time to a particular event will be carried out using the Kaplan-Meier method, and the analysis of differences between groups will be calculated with the log-rank test. The Cox proportional-hazard model will be used to estimate the hazard ratio and 95% confidence interval (CI). Propensity score matching methodology will be used to generate the comparison group from the clinical records. A p-value less than 0.05 will be required to establish significance. All analyses will be performed using SPSS and GraphPad Prism software.

SECTION 5 - ANONYMITY AND CONFIDENTIALITY OF DATA

The data will be obtained from the healthcare center assigned to treat positive cases of COVID-19, through the clinical record designed as an instrument for this study. The laboratory and imaging test reports, as well as the clinical records, will be digitized and sent to the principal investigators using the SOPHOS encryption software. This last part will ensure the confidentiality of each patient's data between devices while transferred. Access will be given to the Dirección General de Vigilancia del Marco Normativo de la Secretaría de Salud de Honduras (General Directorate for Regulatory Framework Surveillance of the Ministry of Health of Honduras) for the monitoring of the study. The hospital will have a password-protected electronic device. The access will be limited exclusively to medical doctors assigned for the study.

The physical documents will be attached to the patient clinical file at the end of the hospitalization.

For the data produced by CT or chest x-ray, the HOROS software will be used to visualize and anonymized DICOM files before sending them to radiologists. The confidentiality in transferring this information will be ensured by using the SOPHOS software.

SECTION 6 - POTENTIAL RISKS AND BENEFITS

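### The protocol gives conflicting end points for data collection (discharge or ICU referral, discharge or death, day 20) and no censoring rule, so 20-day survival is not validly estimable if the earliest is followed

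*Combined protocol and SAP*

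**What the plan says.** All references are to Version B unless stated.

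- **Section 4.1, Administration of thymic peptides:** "If the patient is discharged, or if they need to be referred to an ICU, all the information will be gathered up to that moment". The same sentence then stops the drug. Version A has this sentence too, and the amendment left it unchanged.
- **Section 2.2:** patients who withdraw or self-discharge are replaced "until 20 patients have reached conclusion either by medical discharge or death within a 20-day hospitalization follow-up". ICU referral is not named as a conclusion. For those who leave early, "Patient data will be used up to the date of voluntary withdrawal or self-discharge".
- **Section 4.1, Secondary Outcomes measures:** "Overall survival defined as the time from the start of treatment until death due to any reason [Time Frame: Up to 20 days". The Summary of Changes confirms that this is the only secondary outcome left.
- **Section 4.1, Primary outcome measures:** recovery is the first day in category 1, 2 or 3 of an eight-category scale within 20 days of enrollment. The scale includes "7, hospitalized, receiving invasive mechanical ventilation or extracorporeal membrane oxygenation (ECMO") and, as category 8, death.
- **Statistical Analysis Plan:** "The analysis of time to a particular event will be carried out using the Kaplan-Meier method", with log-rank and Cox comparisons against propensity-matched hospital records. It states no censoring rule and no handling of death in the recovery analysis.
- **Section 5:** data come from the treating centre "through the clinical record designed as an instrument for this study". The paper record is filed when the hospitalization ends.

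No section says how vital status is obtained after ICU referral or after discharge.

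**The concern.** The plan gives three answers to one question: when does observation of a patient end? It is discharge or ICU referral in the dosing paragraph, discharge or death in section 2.2, and day 20 in the survival definition.

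Survival carries weight here. It is the sole secondary outcome, and section 6.3 gives lower mortality as the ultimate aim. Patients referred to an ICU are plausibly those most likely to die. If their record closes at referral, the Kaplan-Meier curve largely describes patients who never needed an ICU. Discharged patients are plausibly at low risk, so removing them from the risk set at discharge distorts the curve in the opposite direction. Kaplan-Meier assumes that censored patients have the same later risk as those who stay under observation, and neither group meets that assumption.

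**Working it through.** The documents give no mortality, ICU-referral or event figure, so there is nothing to reproduce. The only input taken from them is n = 20 (section 2.1). Every other number below is an assumption.

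**1. Bound with no assumed rate.** If m of 20 patients have unknown day-20 status, the lowest possible mortality counts all of them alive and the highest counts all of them dead. The width is m/20, so each patient adds 1/20 = 5 percentage points.

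**2. Hand example, ICU referrals censored.** Assume that 4 of 20 are referred on day 4 and censored, 1 of the other 16 dies on the ward on day 8, and discharged patients are counted alive to day 20.
- Kaplan-Meier mortality = 1/16 = 6.25%, whatever happens in the ICU.
- True mortality = (1 + k)/20, where k of the 4 referred patients die by day 20: 5% for k = 0, 15% for k = 2, 25% for k = 4.

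**3. Same example, discharges also censored.** The dosing paragraph treats discharge and referral alike. If d patients have been discharged and censored before day 8, the single death is weighed against 16 − d patients, so Kaplan-Meier mortality = 1/(16 − d): 6.25% for d = 0, 12.5% for d = 8, 25% for d = 12. The true value is still 5-25% if nobody dies after discharge.

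**4. Large-sample check of direction.** True mortality = p·q + (1 − p)·w, where p is the share referred to ICU, q the share of those who die by day 20, and w the share of the others who die. The Kaplan-Meier values come from simulations of 200,000 patients per scenario. Assumed timings are referral on days 1-7, ICU death 1-12 days later, ward death on days 2-14, discharge on days 4-14, and no deaths after discharge.

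| p, q, w | True 20-day mortality | ICU referrals censored, discharged counted alive | Both censored |
|---|---|---|---|
| 10%, 30%, 10% | 0.03 + 0.09 = 12.0% | 9.8% | 24.1% |
| 20%, 50%, 5% | 0.10 + 0.04 = 14.0% | 4.8% | 12.8% |
| 30%, 70%, 5% | 0.21 + 0.035 = 24.5% | 4.6% | 12.4% |

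Over 27 combinations (p 10-30%, q 30-70%, w 0-10%), censoring ICU referrals alone understated mortality every time, by about 2 to 21 points. With both censored, the error ran from about 12 points too high to 21 points too low.

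**5. Recovery.** Discharge itself meets category 1 or 2, so medical discharge loses little for this outcome; ICU referral does. In the step 2 example, assume that the other 15 ward patients recover, none before day 4, and that the ward death is held as not recovered. Censoring the referred patients gives 15/16 = 93.75%. Holding them as not recovered gives 15/20 = 75%. The truth is (15 + r)/20 = 75-95%, where r of the 4 recover by day 20. If the ward death were also censored and later recoveries followed, the estimate would reach 100%.

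**The case against.** The strongest reply is that the sentence sits under drug administration and was meant only to say when dosing stops. Other text suggests that observation continues. Section 2.2 ends participation at discharge or death, not at ICU referral. Section 5 files the paper record when hospitalization ends. The imaging section plans for intubated patients, using the ventilator console. The recovery scale has categories for invasive ventilation and death.

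This stands as far as intent goes. A reader might infer that ICU deaths will certainly be lost, and the documents do not support that; they support an unresolved conflict. The reply does not remove the conflict. The sentence limits all information, and stopping the drug is a separate clause. Section 2.2 itself ends at discharge, and no section sets up a day-20 status check.

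Three further inferences should also be resisted.
- **A fixed overstatement of survival.** The one-directional shortfall in step 4 needs ICU referrals censored but discharges carried alive, a mixture that no section describes, and it uses assumed rates.
- **A biased comparison with controls.** The controls' follow-up is not stated. If it is cut off in the same way, the two errors may partly cancel, but that would also need adequate matching and similar referral practice. Absolute survival would still be wrong.
- **Lost safety events.** The safety outcomes, such as "Number of participants who experience severe side effects as defined by the GASE", also run up to 20 days. However, both are headed as treatment related, dosing stops at the same moment, and the 20 days may be a ceiling. No loss is claimed here.

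**Conclusion.** Sections 2.2 and 4.1 are inconsistent on when data collection ends, and the Statistical Analysis Plan does not settle the matter. This rests on the text alone. It is conditional that, if the dosing-paragraph sentence is followed literally, deaths after ICU referral or discharge are not captured and Kaplan-Meier does not validly estimate 20-day survival.

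The only size free of assumed rates is 5 percentage points of possible mortality per patient of unknown status. The contrast of 6.25% with 5-25% rests on assumed counts. Censoring ICU referrals alone generally understates mortality when referred patients are at higher risk. Censoring discharges as well can push the estimate up. The net direction and size therefore cannot be derived from the documents, and no hazard ratio or false-positive rate is claimed. The point should be fixed: it affects the sole secondary outcome, and the remedy is small.

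**What to change.** - **Section 4.1, Administration of thymic peptides:** separate the end of data collection from the end of treatment. Record day-20 vital status and ordinal category for every dosed patient regardless of ICU referral or discharge, from hospital or ICU records or by one contact, subject to consent and to the data-use limit in section 2.2. Align the section 2.2 wording.
- **Registry controls:** apply the same 20-day window, and state what the registry holds after referral or discharge.
- **Statistical Analysis Plan, survival:** censor only at day 20 or at the end of permitted data use, and report the number with unknown day-20 status.
- **Statistical Analysis Plan, recovery:** keep ICU-referred patients and deaths as not recovered through day 20 unless category 1-3 is met.

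The cost is a short amendment, a record request or one contact for about 20 patients, the same window for controls, and possibly a change of consent wording. The telemedicine link in section 3 is described only for recruitment, so its use for follow-up would have to be added. The Summary of Changes describes length of stay as already analyzed, so follow-up may be over. In that case, retrieve status from records and report what is missing.

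Separately, sections 4.1 and 6.1 provide for dosing intubated patients by nasogastric tube, while section 4.1 stops the drug at ICU referral. These passages must be reconciled; no view is taken on which is right.
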